- If **advertising** for subjects, describe the process and attach to this form any letters to be sent, texts of advertisements or other material to be used in recruitment. If not available now, this material must be approved by the IRB before use.

We will not be advertising at this time. If we decide to advertise, we will submit material to the NKI IRB for approval first.

- If **screening** patient medical records to identify possible subjects, please so indicate below and complete the form “**Request for HIPAA Waiver of Authorization and/or Waiver of Consent under 45 CFR 46.116(d)**”.

Screening will be done by staff in our division. A HIPAA Waiver of Consent is attached and a phone screening script.

We will use the phone screen to call outpatients that have been referred to us by the Volunteer Recruitment Program (VRP) at NKI. The Volunteer Recruitment Program at NKI recruits from NYS office of Mental Health facilities. The VRP recruits outpatients living on the grounds at CLUE I and II, Conway House(Loeb House), from Rockland County Department of Mental Health facilities and from the community. We will use the phone screen to see if the outpatient is interested in participating in the study and to obtain any screening information specific to this study. We will also use the phone screen to call outpatients who have participated in IRB approved studies conducted by [name]., Ph.D., (those who have agreed to be recontacted for other studies) to see if they are interested in participating in this protocol and if they are willing to answer phone screening questions. We do not have a treating relationship with these potential outpatients. If the outpatient meets phone screen criteria and agrees to come in and sign consent and the HIPAA addendum to participate in the study, prior to starting the intervention, we will to speak with the outpatient’s psychiatrist about the study,

the outpatient's participation in the study(whether there is any issue with the subject participating in the study) and whether the psychiatrist's plans to keep the outpatient's medications stable.

We will also use the phone screen for outpatients who call from the community (i.e. saw study on Clinical trials.gov). If the outpatient is interested in participating in the study and in answering phone screening questions, we will obtain screening information. We do not have a treating relationship with these potential outpatients. If the outpatient meets phone screen criteria and agrees to come in and sign consent and the HIPAA addendum to participate in the study, prior to starting the intervention, we will need to speak with the outpatient's psychiatrist about the study, the outpatient's participation in the study(whether there is any issue with the subject participating in the study) and whether the psychiatrist plans to keep the outpatient's medications stable.

For CREF inpatients, we should be able to get the phone screen information from the medical records or the patient's treating psychiatrist on CREF. However, if we are unable to get screening information from medical records or patient's psychiatrist, we may need to speak to the patient on CREF and talk to them about the study and their willingness to answer some study specific screening questions. We will also speak to the treating psychiatrist about the patient's participation in this research (whether there is any issue with participating in the study and whether the psychiatrist plans to keep the patient's medications stable).

- If recruiting by **other means**, such as referrals from community physicians, please describe below.

We will not be actively recruiting from community physicians, however, we will accept referrals from the community (physicians, friends, and family of the patients).

We will use the phone screen for outpatients who call from the community (i.e. saw study on Clinical trials.gov). If the outpatient is interested in participating in the study and in answering phone screening questions, we will obtain screening information. We do not have a treating relationship with these potential outpatients. If the outpatient meets phone screen criteria and agrees to come in and sign consent and the HIPAA addendum to participate in the study, prior to starting the intervention, we will need to speak with the outpatient's psychiatrist about the study, the outpatient's participation in the study(whether there is any issue with the subject participating in the study) and whether the psychiatrist plans to keep the outpatient's medications stable.

D. RISKS AND BENEFITS:

1. Describe the risks presented by study procedures and interventions, including the expected frequency of the risks. Include all physical and nonphysical risks. (e.g., emotional distress, economic harm, legal jeopardy, breach of confidentiality).

Risks are described above in item 5. Risks

2. If the research presents more than minimal risk to subjects, describe all measures designed to minimize the risks. When applicable, describe inclusion, exclusion and drop-out criteria intended to minimize risks and describe any procedures for follow up such as when subjects are found to be in need of medical or psychological referral.

Minimizing risks are described above in item 5 . Risks

3. Describe any potential for direct benefit to individual subjects as well as the benefit to society based on the scientific knowledge to be gained. These two types of benefits should be clearly distinguished in your discussion.

E. CONSENT PROCESS AND PATIENT CAPACITY:

1. Indicate Who Will Obtain Consent, Assess Capacity, and Under What Circumstances:
(Include name and title of these individuals)

Consent for this project will be obtained by [name], MA, [name]. or [name], M.A. All have had consent training through the Clinical Research Division. Capacity will be assessed by a Treating Psychiatrist or licensed professional who is not directly involved in the research. Capacity will be assessed by Drs. [name], [name] or his designee in the Outpatient Research Division or [name].

2. Will Individuals Potentially Lacking Capacity to Consent be Considered for Inclusion As Subjects:

No. Patients who lack capacity will not be considered for inclusion in this study. Capacity will be assessed by the Treating Psychiatrist or licensed professional who is not directly involved in the research.

If yes, list name(s) and title(s) of persons who will assess capacity (Note: The person(s) who assess capacity must be a psychiatrist or a licensed psychologist who is independent of the research.):

Capacity will be assessed by [name], [name] or his designee in the Outpatient Research Division or [name].

F. COMPENSATION:

Will subjects receive any compensation? Yes No
If yes, indicate how much and criteria for payment. Include method of pro-rating payment, if any, for subjects who do not complete the study.

Subjects will be paid \$20 for the eligibility screening, \$60 for the pre training behavioral assessments, and \$30 (\$10 per hour) for completion of the EEG research procedure and \$5 for the blood draw. Subjects will be paid \$10 per tDCS/training/discussion/and assessment sessions (34 sessions) for a total of \$340 and \$60 for the post behavioral assessments and \$30 for completion of the post EEG and \$5 blood draw. Subjects who complete the study will be paid a

bonus of \$50. The maximum total amount for the whole study will be \$600. Participants will be paid for the time completed. They will not receive the bonus if they do not complete the study.

- G. CONFIDENTIALITY:** Describe means by which privacy of both paper and electronic files will be protected and confidentiality maintained. If a Certificate of Confidentiality will be obtained, please indicate.

Note: All study data whether on paper or in encrypted electronic records or devices must be stored in locked files in a secured office. All electronic data containing PHI must be kept on the “HIPAA drive” or, when portability is required, on a hardware-encrypted device that has been approved by ISD.

Research information obtained will not be identified with participants’ names; we will use a code. All paper data will be kept in locked cabinets and in locked offices. Electronic data will be stored in a HIPAA password protected directory. Any behavioral data that is collected on laptop computer will be collected on an ISD approved laptop that has been encrypted and has password protections which have been put into place by ISD.

- H. CONFLICT OF INTEREST:** In order for the IRB to determine whether financial interests pose a potential for bias that might affect the rights and welfare of the human subjects or the credibility of the research, please briefly describe any financial relationship the principal investigator or other researchers on this project may have with the study sponsor (other than funding this project) or any financial interest in the product being tested.

(Note: “No conflict of interest” or “N/A” is not responsive to the question being asked. The question asks about financial relationships with the sponsor or financial interests in the product. These interests and relationships need not be conflicts. If no relationships or interests exist the answer should be “None” or a similar response.)

None.

- I. OTHER ISSUES:** Does this protocol raise any other sensitive issues concerning human subjects which would be of concern to the IRB or NKI Administration? If so, please elaborate.

No.

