All IRB submissions must be accompanied by a submission abstract. The abstract, at a minimum, should include the elements as per below. Be complete yet concise; restrict your abstract to 2 pages, and expand on the components in the abstract in the other sections of this application as required.

Outline of the IRB Submission Abstract

1. Brief Introduction (2-3 sentences)
2. Specific Aims/Hypotheses (list and explain in bulleted format)

3. Research Participants
 - a. Number
 - b. Method for Ascertainment
 - c. Inclusion/Exclusion Criteria
 - d. Relevant safety cut point (s) for dropping subject from the study
4. Research Procedures
5. Risks
6. Consent Process
7. State whether any drugs tested are approved by FDA, are under an IND (Investigational New Drug Application), or are marketed products being used “off-label”.
8. State whether any devices are under an IDE or Abbreviated IDE
9. Issues requiring special attention of the IRB

1. Abstract of Protocol:

Schizophrenia is associated with impairments in basic auditory functions, such as the ability to match tones following brief delay. These impairments contribute to difficulties that patients have in detecting emotion based on tone of voice (auditory emotion recognition, AER) along with other auditory functions such as sounding out words during reading (phonological processing). Schizophrenia patients also have difficulty in benefiting from remediation exercises designed to correct these deficits.

Transcranial direct current stimulation (tDCS) is a form of non-invasive brain stimulation in which low level electrical currents are applied to the scalp in order to manipulate brain function. In the present study, tDCS will be paired with auditory training to remediate deficits in basic auditory function in schizophrenia with the goal of assessing the tolerability and feasibility of this approach.

Patients will receive 34 sessions of auditory remediation over approximately 12-17 weeks. A total of up to 60 individuals will be enrolled and of the 60, it is anticipated that 45 individuals with a diagnosis of DSM-IV Schizophrenia or Schizoaffective Disorder who have auditory sensory deficits (as reflected in a score of <65% correct on the tone matching task) will complete the study. Patients will be randomly assigned to one of 3 groups: 1) auditory remediation with active tDCS; 2) auditory remediation with sham tDCS; 3) computer video-game remediation.

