IQ\geq75	WRAT, Clinical evaluation, medical history
Score <65% on tone matching	Tone Matching Test
Normal Hearing	Audiometry testing, examination corresponding to a reduction of 1.5 sd vs. HV
Receiving stable antipsychotic medication for >2 weeks	medical history, medication records, clinical evaluation (criteria used in prior studies)

Exclusion Criteria	Method to ascertain
Serious neurological disorder or medical condition/ treatment known to affect the brain. Neurological Disorder that affects the central nervous system (CNS), such as epilepsy, neurodegenerative disorders, movement disorders and sensory disorders.	Clinical evaluation, medical history
Active suicidal ideation	Affirmative answers to items 3, 4 or 5 of the Suicidal ideation section of the screening and pre testing Columbia Suicide Severity Rating Scale (CSSRS) in the 6 months prior to screening or subject who represent a significant risk of suicide in the
Current or past history (within last 6 months) of substance abuse or dependence (excluding Nicotine)	Clinical evaluation , medical history, urine toxicology, SCID
Pregnancy or breastfeeding	Urine Pregnancy Test, self report, medical records
Taking Adjunctive anticholinergic medication (i.e. Cogentin, Benztropine)	Clinical evaluation, medical history, medication records, self report
Participation in study of investigational medication within the past 4 weeks (prior to screening) or investigational device within the past 4 weeks (prior to start of tDCS training)	Self report

d. Relevant safety cut point (s) for dropping subject from the study

Subjects will be withdrawn from the protocol by the study clinician, if any of the following should occur:

-The subject experiences a clinically significant adverse event, which, in the clinical judgment of the investigators/study clinician, would increase the risk to the welfare of the subject and be inconsistent with continuation in the study.

-Clinical worsening: Clinical worsening will be defined as a > 20% increase in PANSS total symptom score from baseline. In the event this occurs, the study clinician will speak with the

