patient, and his/her treating psychiatrist will be notified. The participant will be referred to their primary psychiatrist for re-evaluation, who will then determine if the patient requires changes to his/her medication regimen and if he/she should continue in the protocol or be exited for safety reasons. Patients who are judged by the study clinician to require emergency intervention due to clinical deterioration will be referred to the local hospital emergency department for further evaluation.

-Pregnancy: If any urine test is positive for pregnancy or the subject reports becoming pregnant, the participant cannot to continue with tDCS training sessions and she will be withdrawn from the study.

-Withdrawal of participant consent

-Subject noncompliance, defined as refusal or inability to adhere to the study schedule or procedures. Missing sessions will be reviewed as to the reasons why and if it is found that the individual is failing to adhere to study requirements a decision will be made as to whether the individual will remain in the study. This will be done on a case-by-case basis.

4. Research Procedures

The present study evaluates tolerability and feasibility of repeated administration of tDCS and auditory remediation alone and in combination.

All participants will receive an eligibility screening, which includes demographics, psychiatric and medical history, SCID, assessment of auditory function and auditory emotion recognition, urine toxicology and, if applicable, pregnancy tests, and related measures (~2 hours).

After consenting and establishing eligibility, each participant will be asked to participate 3 behavioral sessions (behavioral sessions can be combine into one or 2 sessions if preferred, each session is ~2 hours or ~ 6 hours total), one ERP/EEG session (~ 3 hours) and a blood draw (~ 5 minutes). These assessments will be repeated at the end of the study, following completion of all training sessions.

Once the assessment sessions are completed, each participant will be assigned randomly to 1 of 3 study arms: 1) active auditory remediation/training + active tDCS; 2) active auditory remediation/training + sham tDCS; 3) computer game condition ("control" remediation). Each training type involves two or three sessions per week, approximately 30 minutes each, for approximately 12-17 weeks (34/30 minute tDCS training sessions) depending on the number of sessions per week the subject is able to attend

1. Eligibility Screening:

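### The $50 completion bonus is forfeited even after a safety or pregnancy withdrawal, a small disincentive to disclosure in a tolerability and feasibility trial

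*Combined protocol and SAP*

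**What the plan says.** **Payment (section F).** Screening, the pre-training assessments, each of the 34 training sessions and the post-training assessments each carry a fee. Fees are pro-rated: "Participants will be paid for the time completed". Completers receive a further $50. For all others the rule is unqualified: "They will not receive the bonus if they do not complete the study". The total is capped: "The maximum total amount for the whole study will be \$600".

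**Withdrawal (section A.3d).** One list of withdrawals by the study clinician covers five grounds:
- an adverse event ("The subject experiences a clinically significant adverse event") that the clinician judges incompatible with continuing;
- clinical worsening, meaning a PANSS total more than 20% above baseline, followed by re-evaluation and a decision to continue or exit;
- pregnancy ("If any urine test is positive for pregnancy or the subject reports becoming pregnant");
- withdrawal of consent;
- noncompliance.

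**Goal (section A.1, Abstract of Protocol).** The study pairs tDCS with auditory training "with the goal of assessing the tolerability and feasibility of this approach". Section A.4 repeats the tolerability and feasibility purpose.

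**The concern.** The first three grounds in A.3d are medical and the last two are matters of attendance or choice, but section F treats all five alike. A participant taken out for a medical reason loses the bonus just as a participant who stops coming does.

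Some of what leads to a medical exit depends on what the participant says. Pregnancy can be established by self-report, and the SAFTEE, C-SSRS and PANSS ratings rest partly on the participant's account. Someone who discloses a problem and is then withdrawn forgoes $50; someone who says nothing and finishes keeps it. The incentive runs towards less disclosure and more completion. Both directions flatter a trial that is meant to find out whether the treatment is tolerable and whether people can finish it. Section A.5 also describes the risk of repeated tDCS in schizophrenia as not yet known, so complete reporting matters here.

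**Working it through.** **1. Reproduce the plan's maximum payment (inputs all from section F).**
- Before training: 20 + 60 + 30 + 5 = $115
- Training: 34 × 10 = $340
- After training: 60 + 30 + 5 = $95
- Subtotal: 115 + 340 + 95 = $550
- With the bonus: 550 + 50 = $600, which matches the stated maximum.

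**2. Size of the amount at issue.**
- Share of the maximum: 50 / 600 = 8.3%
- In session payments: 50 / 10 = 5 sessions

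**3. Set the bonus rule against the grounds for leaving.**

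| Ground in A.3d | Medical reason? | Bonus under section F |
|---|---|---|
| Adverse event | Yes | Lost |
| Clinical worsening, if exited | Yes | Lost |
| Pregnancy | Yes | Lost |
| Withdrawal of consent | Not necessarily | Lost |
| Noncompliance | No | Lost |

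Nothing elsewhere in the supplied text restores the bonus for the first three rows.

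**4. Upper bound on the cost of an exception.** The plan projects 60 enrolled and 45 completers (sections A.3a and B).
- Projected non-completers: 60 − 45 = 15
- Ceiling: 15 × $50 = $750

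The documents do not split the 15 by reason, so $750 applies only if every one of them is a safety or pregnancy exit.

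**5. What cannot be computed.** The documents give no data on how payment affects reporting or retention. Only the direction can be stated.

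**The case against.** The strongest reply is that reporting in itself costs nothing; only withdrawal does, and most reports lead first to review. High Wong-Baker scores go to the principal investigator for review of procedures. A PANSS rise of more than 10 points leads to case review and possibly a temporary pause. A rise above 20% leads to re-evaluation before any exit. Detection also does not rest on volunteered reports alone. There are monthly urine pregnancy tests, biweekly ratings by trained raters, observation during stimulation, contact with treating clinicians, and an independent safety officer who reviews the ratings biweekly. All of this stands, and it keeps the point small. It does not supply a reason to withhold the bonus after a medical exit, and the protocol gives none.

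A reader might infer more than the documents support, in four ways:
- **A larger sum.** A participant withdrawn after session 17 ends $315 short of the maximum. Of that, 17 × 10 + 95 = $265 is pay for sessions and assessments not attended, which is ordinary pro-rating. Only $50 comes from the bonus rule.
- **Lost final assessments.** The post-training assessments carry their own $95, and the plan schedules them only after training is finished. Any gap for early exits lies in the visit schedule, not in the bonus sentence.
- **A penalty for reporting discomfort.** Discomfort as such is not a ground for withdrawal in A.3d. That route runs mainly through the participant's own choice to stop.
- **A biased comparison between arms.** The rule is the same in all three arms, and the documents give no basis for a differential effect.

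**Conclusion.** The point holds, and it is minor. Section F states a rule, rather than leaving a gap, that takes $50 from participants withdrawn for an adverse event, clinical worsening or pregnancy. In a tolerability and feasibility trial this is a small disincentive to disclose problems that may end participation. Its effect on reported tolerability or on completion cannot be sized from the documents, and the monitoring safeguards limit it.

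The conclusion rests on two assumptions. First, a participant withdrawn during training counts as a non-completer for payment; section F does not define completion, but no natural reading says otherwise. Second, the consent form contains no exception. Consent pages are not in the supplied text, so this could not be checked; if an exception exists there, section F should be brought into line with it.

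**What to change.** Amend the bonus sentence in section F so that the $50 is not forfeited when a participant is withdrawn for an adverse event, clinical worsening or pregnancy under A.3d. Name these three grounds. Referring only to withdrawal by the study clinician would not be enough, because A.3d puts noncompliance and withdrawal of consent under the same heading. Non-attendance and other voluntary withdrawal would still forfeit the bonus. Make the consent wording match.

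Two wider remedies are better left out. Making the bonus depend on a final assessment would add a visit that the plan does not provide for early exits. Paying it to anyone who gives discomfort as the reason for stopping could bias tolerability reports the other way.

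Cost: an IRB wording change, no change to the $600 individual maximum, and at most $750 in total. The drawback is that small cost and a marginally weaker incentive to finish.
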